8.0 STUDY MEASUREMENTS AND PROCEDURES

See section 3.0 Study Flow for details on study procedures between screening and study completion. The below tables document the study timeline and schedule divided between PWD and CG study protocols.

PWD Timeline and Schedule				
Interview/Data Collection	Screening (1 week)	Baseline (within 2 weeks after screening)	Treatment or Control Period (Tx; 8-10 weeks; C: single session)	Follow-Up (within 2 weeks of completion of intervention period)
Informed Consent Form	X			
Confirm Age 50+ (Screening)	X			

Confirm Read & Speak English (Screening)	X			
Confirm Dementia Symptoms or Diagnosis (Montreal Cognitive Assessment; MOCA)	X			
Confirm Exclusion Criteria Do Not Apply	X			
Enrollment (if eligible)	X			
Service Availability Measure (SAM)		X		X
Care Values Scale		X		X
Preferences for Care Tasks Scale		X		X
Dyadic Relationship Scale (DRS)		X		X
Personal and Instrumental Activities of Daily Living (PADL & IADL)		X		X
Emotional-Intimacy Disruptive Behavior Scale (EIDBS)		X		X
Dementia Quality of Life +/- Affect		X		X
Center for Epidemiological Studies Depression Scale (CES-D)		X		X
Leisure & Healthy Behaviors		X		X
Quality of Life – AD (QoL-AD)		X		X
SHARE Care Plan (Treatment ONLY)			X	
Resource List (Control ONLY)			X	
Post-Session Evaluation (1 – Control; up to 6 – Treatment)			X	
Treatment Fidelity / Acceptability Measures			X	
Satisfaction Questions				X

CG Timeline and Schedule				
Interview/Data Collection	Screening (1 week)	Baseline (within 2 weeks after screening)	Treatment or Control Period (Tx; 8-10 weeks; C: single session)	Follow-Up (within 2 weeks of completion of intervention period)
Informed Consent Form	X			
Confirm Age 50+	X			

(Screening)				
Confirm Read & Speak English (Screening)	X			
Confirm Dementia Symptoms or Diagnosis (Dementia Rating Scale)	X			
Confirm Exclusion Criteria Do Not Apply	X			
Enrollment (if eligible)	X			
Service Availability Measure (SAM)		X		X
Care Values Scale		X		X
Preferences for Care Tasks Scale		X		X
Dyadic Relationship Scale (DRS)		X		X
Personal and Instrumental Activities of Daily Living (PADL & IADL)		X		X
Personal and Instrumental Activities of Daily Living (PADL & IADL)		X		X
Emotional-Intimacy Disruptive Behavior Scale (EIDBS)		X		X
Dementia Quality of Life +/- Affect		X		X
Center for Epidemiological Studies Depression Scale (CES-D)		X		X
Stress in Providing Care		X		X
Leisure & Healthy Behaviors		X		X
Quality of Life – AD (QoL-AD)		X		X
SHARE Care Plan (Treatment ONLY)			X	
Resource List (Control ONLY)			X	
Post-Session Evaluation (1 – Control; up to 6 – Treatment)			X	
Treatment Fidelity / Acceptability Measures			X	
Satisfaction Questions				X

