5.2 Participant Retention

Missing data and attrition are expected. We conservatively estimated missing data of 10% of the entire sample and potential attrition of 20%. Thus, we are recruiting 120 dementia dyads for Aim 4 to yield a minimum final sample of around 100 AA dementia dyads. To promote retention between data collections, we will send "thank you" notes, birthday cards, and holiday greetings. Members of the research team will establish a positive rapport and good working relationships with participants to reinforce participation throughout the study period. In addition, participants will receive a \$25 honorarium for participating in data collection in each data point (baseline and follow-up).

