- You are encouraged to refer potential families to the study. To do so, you would complete the **Consent to Contact Form** located in the Resourced folder in Teams Channel, and send to [contact]. [name] will contact the family within a week and screen them for eligibility for the study.
- You may or may not be assigned your referred cases. These decisions will be made by the research team on a case-by-case basis.

CASE SCHEDULING

General Notes:

- Please **contact family within 48 hours of assignment** to schedule first (or only) session and immediately email [contact] of scheduled session.
 - If session is not scheduled within 48 hours of assignment, please contact research staff at [contact] to us know the status (haven't called yet, left a message, unable to contact, wrong number, etc...) and repeat every 48-hour interval until session is scheduled.
 - If you are not able to schedule the family within two weeks of assignment, the case will be turned back over to us. The SHARE team will discuss the next steps. Decisions will be made on a case-by-case basis and you will be informed of the status of the case once decisions are made.
- **Treatment Group:** Each subsequent session must be scheduled with the family at the end of a completed session - or you may choose to schedule the entire program at once if that works for both counselor and family. When the SHARE Counselor completes their documentation within 48 hours of the completed session **[See Treatment Data Collection Procedures below]**, the SHARE Counselor will have a space to list the date and time of the next scheduled session.
- **Control Group:** Upon completion of the control family's single session, the SHARE Counselor emails research staff letting them know of case completion at [contact]. Upload the completed electronic case file within 48 hours of the completed session **[See Control Data Collection Procedures below]**. At this point, the SHARE Counselor is completed with this case.

DATA COLLECTION PROCEDURES

Treatment

General Notes:

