11.0 FOLLOW-UP

The intervention period in this low-risk study of a non-pharmacological intervention is just three months in length. As such, follow up is not required. The final point of contact for all dyads will be the post-treatment assessment / interview. Upon completion of the study, there will be no follow-up required.

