13.0 SAFETY REPORTING

[name] and [name] (PI and Consultant) will be responsible for ensuring participants' safety on a daily basis during their participation in Aim 4. Data and safety monitoring will be assured by the study's Research Team Senior key personnel: The PI and study consultants, [name] and [name], are experts in the field of dementia/chronic illness and dyadic research. Along with [name], they will make up the study's Data and Safety Monitoring Committee (DSMC). This team will act to monitor participant safety, evaluate the progress of the study, review procedures for maintaining the confidentiality of data, the quality of data collection, management, and analyses.

[name], [name], and [name] will be informed of any serious adverse events as soon as they occur and will notify the Institutional Review Board of record within 24 hours of notification. The DSMC will meet quarterly with members of the research team either in-person or by teleconference to review the study's progress, review data quality, and participants' safety. At these meetings, an evaluation of the progress of the study will be reviewed, including periodic assessments of data quality, timeliness of recruitment, the appropriateness of the strategies for recruiting participants into the study, assessing the participants' risk in using SHARE materials, and other factors that might affect the study's outcomes.

In the event of an adverse reaction, the DSMC will meet within 24 hours and the following information will be reviewed:

- Participant's study status
- How the participant was recruited into the study and the efforts that took place to retain him/her.
- The nature of the adverse reaction and a determination of how the participant's safety has been threatened as a result.
- A recommendation for how to treat the adverse reaction. In most cases, a recommendation would be to discontinue the individual's participation in the intervention and/or to withdraw the participant from the study. In more severe cases, the participant might be referred to an identified expert (the Alzheimer's Association, a geriatric care manager or licensed clinical social worker, etc.).
- If the adverse reaction is deemed to be very serious (i.e., suicidal risk or the health/well-being of the participant is in jeopardy), the case will be reported to the appropriate authorities to intervene on the situation immediately.

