14.0 STUDY COMPLIANCE

The PI will maintain a Protocol Deviation / Violation Log, in which she will report of all protocol deviations/violations. All such deviations / violations will be reported to the Data and Safety Monitoring Committee (DSMC), including but not limited to the following:

- Enrollment of an ineligible participant
- Failure to obtain Informed Consent
- Visits or procedures conducted outside of the protocol specified window
- Failure to keep IRB approval up-to-date
- Wrong treatment administered to participant
- Follow-up visit at a time point different from that specified in the protocol

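### Follow-up is tied to the end of each arm's own period, so control dyads are measured at about 0–2 weeks and SHARE dyads at about 8–12 weeks after the first session

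*Protocol*

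**What the plan says.** In Protocol section 8.0, the tables for the person with dementia and for the caregiver carry the same column headings. The middle column reads "Treatment or Control Period (Tx; 8-10 weeks; C: single session" and the last reads "Follow-Up (within 2 weeks of completion of intervention period". Outcome measures are taken at baseline and in that last column only.

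Three other sections bear on timing:

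- **Section 11.0** says that "The intervention period in this low-risk study of a non-pharmacological intervention is just three months in length", without splitting by arm, and that "The final point of contact for all dyads will be the post-treatment assessment / interview".
- **Case Scheduling** (in the counselor procedures after section 9.0) says, once a control family has had its one session, "At this point, the SHARE Counselor is completed with this case".
- **Section 14.0** lists among reportable deviations "Follow-up visit at a time point different from that specified in the protocol".

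Section 13.0 says that after an adverse reaction the usual recommendation would be to end "participation in the intervention and/or to withdraw the participant from the study". A dyad can thus stop SHARE and remain in the study.

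**The concern.** A randomised comparison needs the outcome measured at the same time in both arms. Here the trigger is completion of a period that lasts two months or more in one arm and a single session in the other.

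The outcomes include depression, quality of life, daily function and caregiver stress, in families living with dementia. Any change in these that has nothing to do with SHARE, whether disease progression, season, adaptation or regression to the mean, has far longer to act in the SHARE arm. If scores worsen over time, SHARE looks worse than it is and a real benefit may be masked. If they improve, SHARE gets credit it did not earn. Aim 4 seeks preliminary efficacy from a trial described as fully powered, so this contrast matters.

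A second consequence follows from the same trigger. A dyad that stops SHARE early but stays in the study never completes the period, so it has no defined interview date and its outcome may be lost.

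**Working it through.** The protocol states no figure for time to follow-up, so there is none to reproduce. It follows from the table headings.

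**Inputs**

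- SHARE period: 8–10 weeks (section 8.0).
- Control period: one session, taken as 0 weeks from first session to completion (section 8.0).
- Follow-up: 0–2 weeks after completion (section 8.0).
- Allocation: 60 per arm (section 7.0).
- Attrition: 20% (section 5.2).

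**Time from first session to follow-up = period length + follow-up window**

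- Control: 0 + (0 to 2) = 0–2 weeks, midpoint 1.
- SHARE: (8 to 10) + (0 to 2) = 8–12 weeks, midpoint 10.
- Gap between midpoints: 10 − 1 = 9 weeks.
- Smallest gap: 8 − 2 = 6 weeks. Largest gap: 12 − 0 = 12 weeks.

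**Does a different starting point help?** Under Case Scheduling, a case not scheduled within two weeks of assignment is handed back, in either arm. Allowing 0–2 weeks from assignment to first session gives 0–4 weeks for control and 8–14 weeks for SHARE. The windows are still disjoint.

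**Can the analysis repair it?** Baseline scores are taken before assignment and carry no information on what happens between week 2 and week 8. With disjoint windows, a time covariate could separate arm from time only by extrapolating a trend estimated within each arm's narrow window.

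**Illustration of size.** The drift rates are assumptions; the protocol gives none.

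- Bias = rate per 12 weeks × gap / 12.
- Dyads per arm: 60 × 0.8 = 48. Unadjusted standard error of the arm difference: √(2/48) = 0.204 SD.

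| Assumed drift per 12 weeks | Bias at 9-week gap | Bias / SE | Two-sided 5% rejection rate with no true effect |
|---|---|---|---|
| 0.1 SD | 0.1 × 9/12 = 0.075 SD | 0.37 | about 7% |
| 0.2 SD | 0.2 × 9/12 = 0.150 SD | 0.73 | about 11% |
| 0.3 SD | 0.3 × 9/12 = 0.225 SD | 1.10 | about 20% |

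The rejection rate is Φ(−1.96 + bias/SE) + Φ(−1.96 − bias/SE). Over the full range of gaps, the bias runs from 0.1 × 6/12 = 0.05 SD to 0.3 × 12/12 = 0.30 SD.

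**The case against.** The strongest counter-argument is that the follow-up heading refers to the intervention period, a term that section 11.0 uses for one study-wide span of three months (about 13 weeks). If that span governed both arms, everyone would be interviewed at about 13–15 weeks and the confounding would vanish. Section 8.0 also refers to the Study Flow in section 3.0, which is not legible in the copy reviewed and might set a common time.

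Neither point rescues the text as it stands. Both tables split the period by arm immediately before the follow-up column, and three months matches neither 8–10 weeks nor a single session. If the Study Flow sets a common time, it conflicts with the natural reading of both tables. On every reading the protocol needs correcting.

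Some lesser objections stand:

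- The Case Scheduling text ends the counselor's task only. Research interviewers collect the outcomes (section 16.0), so it is weak evidence on interview timing.
- The deviation rule in section 14.0 counts against a later control call only once the tables are read as above.
- The drift rates are chosen, not sourced, so only the gap in weeks rests on the document.
- Acceptability and feasibility, the other half of Aim 4, are little affected.

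**Conclusion.** The concern holds and should be fixed before follow-up interviews begin. As the tables are written, arm and time to follow-up are fully aligned: 0–2 weeks against 8–12 weeks from the first session, with a gap of 6 to 12 weeks and no overlap. This rests on reading the follow-up trigger as the end of each arm's own period, which is what both tables say, and on counting the single control session as zero weeks.

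The size and direction of the resulting bias cannot be derived from the protocol. Under the assumed drifts it is between a third of a standard error and slightly more than one. No control measurement is planned after the early interview, so the missing information cannot be recovered once the data are in, whatever the SAP specifies.

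**What to change.** 1. In both section 8.0 tables, replace the completion-based trigger with one follow-up window counted from baseline or assignment, identical in both arms. Place it to cover the expected end of SHARE: the planned lag from the chosen anchor to the first session, plus the stated SHARE period. For example, with assignment as anchor and a first session within two weeks, the latest on-schedule finish is 2 + 10 = 12 weeks, so the window would open at week 12.
2. Hold the interview in that window for every randomised dyad that has not withdrawn from data collection, however many sessions were completed, and record that number.
3. Reconcile section 8.0, section 11.0 and the Study Flow so that they state the same period length and follow-up time. Section 14.0 then refers to the new window.

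**Cost.** Amendment wording and a later call for control dyads, with no added interviews. Control attrition may rise slightly because of the longer wait. Control dyads would answer the satisfaction items at follow-up some weeks after their one session, though the post-session calls already capture early impressions. A few SHARE dyads that run late would be interviewed before finishing, which is acceptable for a comparison of the arms as randomised.

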9.0 TIMELINE AND SCHEDULE

Project Activities	Year 1				Year 2			
	Project Quarter				Project Quarter			
	1	2	3	4	5	6	7	8
A. Stage 1A								
1. Prepare SHARE for Dementia materials for review [Aim 1a].								
2. Recruit Advisory Council members [Aim 1a].								
3. Convene Advisory Council [Aim 1a].								
4. Adapt SHARE based on AC feedback [Aim 1b].								
5. Recruit sites/subjects for focus groups [Aim 2].								
6. Convene focus groups [Aim 2].								
7. Analyze focus group data [Aim 2].								
8. Revise SHARE and prepare Version 2 for testing [Aim 2].								
B. Stage 1B								
1. Recruit SHARE Counselors to be trained [Aim 3].								
2. Conduct SHARE Counselors Training (n=20) [Aim 3].								
3. Conduct clinical trial (n=120 African American dyads; 60 treatment/60 control) [Aim 4].								
4. Analyze results [Aim 4].								
5. Prepare final report & continue dissemination activities [Aim 4].								

SHARE COUNSELOR PROCEDURES

The Basics

SHARE Training Webinar

The goal of this training webinar is to familiarize SHARE Counselors with the SHARE for African Americans study and procedures related to recruitment and referral, enrollment, assignment, scheduling, and data collection.

The following materials will be reviewed:

- Contact Release Form
- Billing and Invoicing
- SHARE Care Values Comparison Tool
- SHARE Care Circles
- SHARE Care Plan

Pre-Training Preparation and Initial Training Requirements:

Prior to this webinar, you will have received and completed the following:

- Introduction call on the project and counselor requirements
- SHARE Counselor Online Training Course
- Human Subjects Protection Training (required to work with research human subjects)

The completion of the training course online will have prepared you to fulfill the role of a SHARE Counselor. For this webinar, the SHARE team will not discuss session specifics but instead focus on putting knowledge of the program to practice through case scenarios.

Microsoft Teams

Personalized Teams Channel

- You will be invited to a private Microsoft Teams Channel by the SHARE Research Team. Only you and the research team will have secure, and privacy protected access to case information housed in this channel
- The channel will be named by your first and last name
- There will be multiple documents within the channel
 - Resources Folder: Will house blank documents and fillable forms
 - Case Assignment Folders: Your case folders will be organized here by ID#/Group Assignment and will contain all the relevant documents for each case
 - Data Submission Folder: Here is where you will upload your completed data files [See Data Collection Procedures below]

Remote Delivery

This is a virtual study with all sessions taking place on a computer or tablet. You and your care partners may choose to use a desktop, laptop, or tablet to participate in sessions.

- SHARE Counselors will use Microsoft Teams to deliver SHARE Treatment and Control sessions with families
- Utilize Teams to create meeting links you will share with your care partners to log into the session
- SHARE Counselors can provide basic technology support to families trying to log in for sessions. Encourage care partners to seek help from other family or friends to help set up their computers/tablets to successfully participate
- If a family continues to struggle with technological aspects of the project, contact [name] at [contact] for assistance.

CASE ASSIGNMENTS

Procedures

Case Assignment Procedures:

Research staff will assign screened and eligible care partners who have been through a baseline research interview to appropriate counselor based on logistics, such as geographic location, referral source, and counselor/family availability and date/time preferences.

- [name]/[name] will send out **one** assignment email:
 1. Will have in the subject line: New Case Assignment: Case #####_Treatment/Control
 2. You will then go to your Microsoft Teams channel and locate the Assignment Info folder. Find the assignment sheet with the ID# from your assignment email.
 3. The assignment sheet will contain the family's contact information along with important details that the counselor needs to know in the notes section (i.e. best person/times to contact, diagnosis, ages of care partners if relevant, important information regarding availability or preferences that are known at the time, etc...).
 4. Within that case's folder in your Teams channel, you will also find the original electronic case file. When you first open that document, you will notice there will be some basic information populated for you. Once you begin your case, you will fill this out each time **[See Data Collection Procedures below]**.

Referrals to the Program

- You are encouraged to refer potential families to the study. To do so, you would complete the **Consent to Contact Form** located in the Resourced folder in Teams Channel, and send to [contact]. [name] will contact the family within a week and screen them for eligibility for the study.
- You may or may not be assigned your referred cases. These decisions will be made by the research team on a case-by-case basis.

CASE SCHEDULING

General Notes:

- Please **contact family within 48 hours of assignment** to schedule first (or only) session and immediately email [contact] of scheduled session.
 - If session is not scheduled within 48 hours of assignment, please contact research staff at [contact] to us know the status (haven't called yet, left a message, unable to contact, wrong number, etc...) and repeat every 48-hour interval until session is scheduled.
 - If you are not able to schedule the family within two weeks of assignment, the case will be turned back over to us. The SHARE team will discuss the next steps. Decisions will be made on a case-by-case basis and you will be informed of the status of the case once decisions are made.
- **Treatment Group:** Each subsequent session must be scheduled with the family at the end of a completed session - or you may choose to schedule the entire program at once if that works for both counselor and family. When the SHARE Counselor completes their documentation within 48 hours of the completed session **[See Treatment Data Collection Procedures below]**, the SHARE Counselor will have a space to list the date and time of the next scheduled session.
- **Control Group:** Upon completion of the control family's single session, the SHARE Counselor emails research staff letting them know of case completion at [contact]. Upload the completed electronic case file within 48 hours of the completed session **[See Control Data Collection Procedures below]**. At this point, the SHARE Counselor is completed with this case.

DATA COLLECTION PROCEDURES

Treatment

General Notes:

All required data collection for the project will be described below with timelines, data sharing procedures, and contact information in case there are issues. For any data collection challenges, please contact Project Coordinator [name] – [contact] or [contact]. For clinical guidance, adverse reactions, or concerns about subject safety, reach out to Principal Investigator, [name]. For non-emergencies, email – [contact] -or- [contact]. For urgent matters, [name] may be reached at [contact].

All SHARE Program Counseling Data Collection Tools for Treatment Group Cases are listed below:

Post-Session Case Notes:

Electronic Case Files: Throughout your sessions, you are expected to take detailed notes in the electronic case file provided to you in your Microsoft Teams channel for each assigned case. You will upload the completed version into the Teams folder for each session within **48 hours** of completion. The electronic case file includes each of the following sections, per session:

- **Session Preparation:** A list of what tools you will need to have reviewed and/or ready prior to that session.
- **Changes Since Last Session:** Here you will report any major changes that either care partner has experienced since the last time you spoke with/met them. This is an important reporting requirement to our funder. If anything, major has occurred, please fill out an **Adverse Event Form** as soon as possible and send it as an encrypted file to [contact] within 24 hours -or- upload it to your Teams Channel.
- **Session Information:** Basic information about the session [date, time of session, session duration, PWD location, CG location).
- **Session Counselor Evaluation:** Each treatment session will include an evaluation of session components from your perspective.
- **Readiness Ratings:** You will rate each care partner's level of readiness at the end of each session and note any important contents to support your rating in the box provided.
- **Session Notes:** Complete notes on your session at the of the case file for that session.

Procedures:

- **Electronic Case File:** Save the document after each completed session and name the most recent case file into the Completed Data Folder for your case using the following convention:
 - #####_Session1_Case File Complete
 - #####_Session2_Case File Complete
 - #####_Session3_Case File Complete
 - #####_Session4_Case File Complete
 - #####_FamilySession_Case File Complete
 - #####_Session5_Case File Complete

At the completion of all sessions, your case should have 5-6 completed case files (5 if there is no family session held).

*You will **NEVER** share the Electronic Case File with the family. This is a research document **ONLY**.

- **Other Fillable Data Forms:**

[You will email these to families using encryption as often as you'd like]

- **Care Values:** We will provide an initial Care Values Comparison document in a Care Values folder for you in your Teams Channel for each case. You will use this document to conduct the Care Values Discussion in Session 1.
- **SHARE Care Circles:** We will provide you with three SHARE Care Circles documents for you in a Care Circles folder in your Teams Channel for each case. Two files will be there for you: PWD's Care Circles and CG's Perceptions Care Circles. You will use then use the PWD's document to conduct the Care Preferences discussions in Session 2. You will resave that document into a new version that will contain the final Care Circles. You will name that document beginning with the ID#: #####_CareCircles_Session2_FINAL.

Data Collection Milestones:

At the end of each session, the following data elements are due in your Microsoft Teams Channel folder in the Completed Data folder within **48 hours** of your session ending:

Session 1:

- Electronic Case file
- Revised Care Values file (if care values were adjusted in Session 1)

Session 2:

- Electronic Case file
- Revised Care Values file (if care values were adjusted in Session 2)
- Revised Care Circles file (demonstrating the new SHARE Care Circles)

Session 3:

- Electronic Case file
- Completed SHARE Care Plan created in Session 3
- Revised Care Values file (if care values were adjusted in Session 3)
- Revised Care Circles file (if care preferences were adjusted in Session 3)

Session 4:

- Electronic Case file
- Completed Family Session Agenda [Counselor Version; the Family version you will send to the family]
- Revised SHARE Care Plan (if Plan changed after having Session 4 discussions)
- Revised Care Values file (if care values were adjusted in Session 4)
- Revised Care Circles file (if care preferences were adjusted in Session 4)

Family Session:

- Electronic Case file
- Revised SHARE Care Plan (if Plan changed after Family Session)
- Revised Care Values file (if care values were adjusted in Family Session)
- Revised Care Circles file (if care preferences were adjusted in Family Session)

Session 5:

- Final Electronic Case file
- Final SHARE Care Plan (if Plan changed after Family Session)
- Final Care Values file (if care values were adjusted in Family Session)
- Final Care Circles file (if care preferences were adjusted in Family Session)

Post Session Email:

Once you are completed with your final session for a case, within 24 hours you will email [contact] that your case is complete and all of your data have been collected.

Evaluations of Your Care Partners:

At the end of each session, a researcher will call the family on the phone and will ask them questions about their experiences. Please remind the family at the end of each session that someone from Benjamin Rose is going to call them to check in. This call will take place within 48 hours of your data being received in the Teams folder, confirming the session took place.

